We designed the present randomized trial to test whether 12 weeks of supervised weekly Kundalini yoga class and a brief daily home meditation practice can improve cognitive function among older women with high AD risk compared to weekly classes of memory training with daily homework. Our choice of interventions is based on prior studies of mind-body exercise in older adults that revealed robust cognitive benefit, as well as our own studies of this intervention compared to cognitive memory training in older adults with MCI. Kundalini yoga has also been observed to impact the frontal lobes, likely due to increased cerebral blood flow ([name] et al., 2013b).

The primary outcome will be memory performance at 12 weeks (i.e., immediately post-treatment).

Secondary outcomes include measures of executive functioning and changes in brain structure and connectivity.

Specific Aim 1: To evaluate effects of Kundalini Yoga+ Kirtan Kriya (KK+KY) and Memory Enhancement Training (MET) on memory performance in women with high AD risk.

Hypothesis 1: Improved memory performance will be observed in women receiving KK+KY and MET at 12 weeks compared to baseline.

Specific Aim 2: To test the efficacy of KK+KY vs. MET for improving executive functioning including working memory.

Hypothesis 2: KK+KY will improve performance in executive functioning to a greater extent than MET.

Exploratory Aim 3a: To test the effects of MET vs. KK+KY on structural and functional connectivity and task-related activation for working and episodic memory.

Hypothesis 3a: Compared to MET, KK+KY will be associated with greater improvement in connectivity in regions associated with working and episodic memory.

Exploratory Aim 3b: To test the effects of MET vs. KK+KY on levels of cellular and genomic markers of inflammation, telomerase activity level, and telomere length after 12 weeks and at 6 and 12 month follow-up.

Hypothesis 3b: Compared to MET, KK+KY will be associated with decreases in cellular and genomic markers of inflammation and increases in telomerase activity level and telomere length after 12 weeks and at 6 and 12 month follow-up.

Exploratory Aim 3c: To explore whether KK+KY results in reduced cardiovascular risk factors compared to MET, and whether this effect will correlate temporally with changes in fMRI measures and clinical outcomes.

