In the fitting method, f(i) is CBF at each individual delay and the final CBF is the mean of the estimated CBF per PLD. The 5 PLDs allow us to estimate CBF and ATT simultaneously using parameters fitting (2). Resulting rCBF and ATT maps will then be co-registered with the T1-weighted structural scan and normalized to the MNI standard space template with subsequent spatial smoothing.

WM Hyperintensities (WMH). The 3D T2-space images will be used to visualize WMHs by employing a semiautomated WMH identifier (Schwarz, Fletcher, DeCarli, & Carmichael). Briefly, WMH burden will be assessed based on the signal intensities of co-registered 3D MEMPR and T2-SPACE images, and population statistics on the spatial distribution and neighborhood structure of WM lesions. With every unit increase in WM burden, we will estimate % reduction in local brain tissue volume. GLM and multiple regression analyses will determine links between WM burden, clinical measures and vascular risk factors in each treatment group that may need to be controlled for.

Integration with Mood and Neurocognitive Measures. To test hypotheses about the relationships between imaging metrics and change in mood and cognition, we will derive domain summary scores for the 3 domains of interest – i.e., mood, memory, and executive functioning. Percent change in the mean Z scores will be calculated for each domain score and entered into analysis. We will first test the specific hypotheses described in the aims using separate GLMs for each MRI method. *Integration of Predictive Variables.* After analysis is complete on the predictive validity of each MRI measure, those that significantly predict remission/relapse or cognitive decline at follow-up will be combined for regression analysis. We will use the best single predictor in each modality. The final analysis will include a step-wise multiple regression analysis of clinical outcomes.

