Autonomic nervous system (ANS) and respiratory measures. In order to link genotype and neuroimaging data with respiratory and ANS functioning, we will perform a series of five tests: 1) rest; 2) paced breathing; 3) breath hold; 4) Valsalva maneuver; 5) hand grip. These tasks will provide detailed information about cardiorespiratory functioning. Continuous blood pressure will be assessed using a probe attached to two fingers of the same hand. An additional finger probe will be used to measure the Galvanic skin response (GSR) and chest electrodes will be applied for the electrocardiogram (ECG) and on the hand for an electromyogram (EMG). A respiratory belt around the patient's chest will provide breath rate data and a small probe attached to the cheek will measure changes in face skin temperature. End-tidal CO2 will be measured using a capnometer and spirometry will be used to investigate pulmonary capacity. Verbal instructions will be provided and a computerized task will indicate to the subjects when to begin and end each challenge, for example when to prepare for the breath hold (deep inhale followed by deep exhale and then hold at the top of the next deep inhale). Data will be recorded and time-locked using a BioPac system and associated software, which will also be used to process the data.

Randomization and treatment schedule:

After all screening and baseline test results are reviewed and eligibility criteria are confirmed, patients will sign the informed consent form. Next, participants will be randomized to either MET or KK+KY groups using a computer-generated random assignment scheme, which assigns participants in a 1:1 ratio to each group using a customized module built into the centralized data system. All behavioral raters will be blind to the group assignment, and participants will be asked not to disclose their group assignment to the raters.

Study intervention procedures:

Participants will be randomized to: (1) MET class for 60 minutes per week plus daily homework; or (2) KY class for 60 minutes per week plus daily KK homework. Participants will complete a questionnaire about their treatment expectations after their second class. Follow-up assessments immediately after the intervention (12 weeks) as well as at 24 and 48 weeks will test the effect of the interventions at both short- and long-term follow-up.

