Data will be analyzed using the SAS (v9.4) statistical package. Data will be examined initially to identify issues such as departures from normality, which might suggest the need for transformation (e.g., logarithmic). Demographic variables (e.g., age, gender, etc.) will be compared by treatment group and examined in relation to outcome variables; this would define one possible set of appropriate covariates, if needed. Correlations (a) among outcome measures and (b) among potential covariates will be examined to eliminate redundancy via possible data reduction, e.g., formation of composite scores or selection of single measures from sets of highly inter-correlated variables. Cognitive domain scores will be obtained as follows: for each neuropsychological test, raw scores will be converted to standardized (Z) scores with a mean of 0 and a SD of 1, based on all participants combined. Then, for each of the tests in a cognitive domain, the Z scores will be averaged to create a single Z score per cognitive domain.

The independent samples *t*-test or Chi-square test will be used to compare the demographic characteristics between the MET and KK+KY control group. The effect of intervention over time on the cognitive functions will be investigated in intention-to-treat (ITT) analyses. Measurements will be analyzed using linear mixed models; analyses will assume missing at random with missingness allowed. All models will include random intercepts to account for correlations between the repeated measures for each participant. The fixed components of the models will include effects of group and time and a group X time interaction, with post hoc analyses between times and groups. All statistical significance tests will be two-sided, and an alpha-level of 0.05 will be considered statistically significant for primary analyses and Bonferroni correction will be employed for post hoc analyses.

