Primary outcome: The analyses for the memory domain Z scores will use general linear mixed model (GLMM) analysis (e.g., SAS PROC MIXED). The two treatment groups will be compared for time course of cognitive domain z scores the initial endpoint EOT at 12 weeks and 6- and 12-months. Covariates may be included in the model as noted above. As noted above, the primary cognitive domain of interest for this proposal is memory. A separate GLMM as above will be estimated using memory domain z-scores as dependent variables. Executive Function will be examined as secondary outcome measure. Supplementary analyses of the follow-up period will look at the cognitive domain scores by treatment group controlling for values at EOT (post-treatment changes). Objective memory measures will be examined using a similar GLMM.

Exploratory Hypotheses: GLMM models as described above will be used to examine telomerase activity (overall level and TL) and inflammatory measures separately. Relationships between changes in markers of inflammation and telomerase activity to changes in cognitive scores, cognitive domain scores and fMRI measures will be examined using regression models within each group. Transformations of the measures will be performed as necessary.

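### Marker, cognition and fMRI changes are related by separate regressions in each arm, which halves the sample and leaves no test of whether a relation differs between yoga and memory training

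*Combined protocol and SAP*

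**What the plan says.** In the Data analysis section, the Exploratory Hypotheses paragraph has two parts.

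- **The markers themselves.** "GLMM models as described above will be used to examine telomerase activity", and the inflammatory measures are handled in the same way. The model referred to has "effects of group and time and a group X time interaction", so it uses both arms together.
- **Relations of marker change to cognitive and imaging change.** Here the plan changes method: changes in cognitive scores, domain scores and "fMRI measures will be examined using regression models within each group". No pooled model, arm-by-marker term or comparison of slopes is named.

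On error rates, the same section says "All statistical significance tests will be two-sided" and "an alpha-level of 0.05 will be considered statistically significant for primary analyses". Bonferroni is assigned to post hoc analyses, Benjamini-Hochberg to the secondary outcomes (Power analysis) and a 5% false discovery rate to differential gene expression (Inflammatory biomarkers). Nothing is assigned to these regressions.

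The Power analysis paragraph expects 90 completers, 45 per arm. The Recruitment paragraph expects 35-36 per arm at 12 months.

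**The concern.** Mechanism of response is a stated purpose of the trial, and the exploratory aims are framed as yoga against memory training. Two separate regressions do not test whether a marker-outcome relation differs between arms. They leave the reader with two p-values, and the natural but invalid step is to compare them. They also give up half the sample when the relation is the same in both arms, which is the case where pooling helps most.

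Two things could go wrong: a moderate relation present in all women is missed, or a relation common to both arms is described as belonging to one.

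**Working it through.** **1. The plan's own figures.** The documents give no power for the exploratory regressions, so the nearest check is the equivalence statement: 45 per arm, margin 0.62 SD, true difference zero, 80% power. With 0.05 for each one-sided test:

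2Φ(0.62/√(2/45) − 1.645) − 1 = 2Φ(2.941 − 1.645) − 1 = 80.5% (79.7% with the t distribution).

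The secondary-outcome figure (effect size 0.60, 80% power) also reproduces, at 80.4% by exact t. The sample size of 45 per arm is therefore used as the plan means it.

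**2. Inputs.**
- n = 45 per arm: 100 enrolled, at most 10% lost, with an allocation scheme "which assigns participants in a 1:1 ratio to each group". Pooled n = 90.
- Two-sided tests, from the Data analysis section.
- Alpha 0.05: assumed, since it is stated only for primary analyses.
- True correlation r of 0.2 to 0.4, the same in both arms: assumed, since the documents give none.

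**3. Formulas.** Power for one correlation by Fisher's z (negligible opposite tail omitted): p = Φ(√(n−3)·atanh(r) − 1.96). At r = 0.3 and n = 45 this is Φ(6.481 × 0.3095 − 1.96) = Φ(0.046) = 52%. At n = 90 it is Φ(9.327 × 0.3095 − 1.96) = Φ(0.927) = 82%.

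The arms are independent, so P(exactly one arm significant) = 2p(1−p) and P(yoga only) = p(1−p).

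| Shared r | Power, one arm (45) | Power, pooled (90) | Exactly one arm | Yoga only |
|---|---|---|---|---|
| 0.2 | 26% | 47% | 38% | 19% |
| 0.3 | 52% | 82% | 50% | 25% |
| 0.4 | 78% | 98% | 34% | 17% |
| 0.5 | 94.5% | 99.9% | 10% | 5% |

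Simulation of 200,000 pairs of arms at r = 0.3 gave 50.1% for exactly one arm and 25.0% for yoga only.

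**4. Detectable correlation at 80% power.** tanh((1.96 + 0.842)/√(n−3)) gives 0.41 for one arm of 45 and 0.29 pooled. With 36 per arm it is 0.45. That last case applies only where a 12-month change is used; Table 4 schedules no telomere, telomerase or expression sample then, although Hypothesis 3b names that visit.

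**5. Direct test of a difference between arms.** z = (atanh r₁ − atanh r₂)/√(2/42). Under a shared relation it rejects 5% of the time (simulated 5.1% at r = 0.3). Its power is Φ(0.5493/0.2182 − 1.96) = 71% for r = 0.5 against 0, and Φ(0.4236/0.2182 − 1.96) = 49% for 0.4 against 0.

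**The case against.** The best defence is that these are exploratory analyses in a self-described pilot. Hypothesis 3b concerns marker levels by arm, and the mixed model tests that with both arms. No hypothesis says that slopes differ. This stands, and it limits the consequence. It does not justify the split: if no difference in slopes is expected, the pooled slope is the better estimate; if one is of interest, it needs a test.

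Stronger readings are tempting, and the documents do not support them.

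- **That a yoga-only finding would arise by chance about half the time.** p(1−p) cannot exceed 25%. The 50% is for a split in either direction, and only near r = 0.3. Given a significant yoga result, the other arm is non-significant in 74%, 48% or 22% of cases at r = 0.2, 0.3 or 0.4, so one half is not a general figure there either.
- **That the plan will report a one-arm result as yoga-specific.** It states no such rule and promises to report all proposed analyses. The risk is only left open. It is not fanciful: the Power analysis paragraph rests conclusions on the pattern of results, and Preliminary data describes the earlier trial by which arm reached significance, although the cited publication may contain a direct comparison.
- **That all mechanism analyses are split by arm.** Exploratory Aim 3c asks "whether this effect will correlate temporally with changes in fMRI measures and clinical outcomes", but about cardiovascular risk factors. The white matter paragraph looks for "links between WM burden, clinical measures and vascular risk factors in each treatment group" in order to find variables to control for. The imaging models under Integration with Mood and Neurocognitive Measures are not said to be within arm.
- **That splitting inflates multiplicity.** As an illustration, 4 markers × 5 domains × 2 arms = 40 independent null tests give 1 − 0.95⁴⁰ = 87% for at least one p < 0.05. The grid and the independence are assumed, and a joint model with a slope and an interaction per pair also has 40 tests. What stands is that no error control is assigned to this set.

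**Conclusion.** The concern holds for the regressions of cognitive and fMRI change on inflammation and telomerase change. Each uses about half the completers, and no test of a between-arm difference in slope is planned. For a shared correlation of 0.2 to 0.4, one arm but not the other would be significant in about 34-50% of cases, and yoga alone in about 17-25%. Pooling raises power from 26-78% to 47-98%.

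These figures are per pair, before any multiplicity adjustment, and rest on the assumed correlations, the assumed alpha of 0.05 and 45 women per arm with complete data. Because attrition is given as at most 10%, 45 is the planned minimum at 12 weeks; with all 50 per arm, power at r = 0.3 would be 56% within an arm and 86% pooled. The primary and secondary conclusions are unaffected.

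**What to change.** Replace the within-group sentence with the following.

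- List the marker-outcome pairs and the visits in advance.
- For each pair, fit one model in all women with arm, marker change and arm × marker change.
- Always report the arm-adjusted common slope (the model without the product term). Report the two within-arm slopes and their difference with confidence intervals as description. Do not let the interaction p-value decide which is reported: with 49-71% power against the differences above, such a pre-test would often average away a real difference.
- Claim an arm-specific relation only from the interaction test, and state that its power is modest.
- Apply the Benjamini-Hochberg method, already planned for secondary outcomes, across the pairs, and say whether common slopes and interactions form one family or two.

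The cost is a change of wording and code, with no new data, visits or participants. Within-arm slopes lose their status as tests, and the interaction estimates will be imprecise.

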Memory Enhancement Training (MET): Memory training is based on the notion that cognition is plastic in older age (A. Acevedo & Loewenstein, 2007). Traditional memory training interventions facilitate plasticity by teaching people mnemonic techniques involving verbal association and visual imagery and practical strategies that boost encoding and retrieval (Gross et al., 2012; Verhaeghen, Marcoen, & Goossens, 1992). A meta-analysis of 33 clinical trials including data from over 1,500 older adults showed that gains on objective memory tests following memory training are large (i.e. on average, a standardized mean difference from pretest to posttest of .73) compared to the small-medium sized effects for control (.37) and placebo (.38) conditions. A more recent metaanalysis (Gross et al., 2012) of 35 studies reported that memory training effects remain significant after controlling for practice effect. The overall estimate of effect size (the mean standardized difference in pre-post change between memory-trained and control groups) was 0.31 standard deviations (SD); the pre-post training effect for memory-trained interventions was 0.43 SD and the practice effect for control groups was 0.06 SD. Effective mnemonic memory enhancement methods involved visual imagery, verbal associations, story mnemonics, organizational encoding strategies, and the use of multiple techniques, and no specific strategy is better than another (Bjorklund, Schneider, Cassel, & Ashley, 1994; Gross et al., 2012; Stigsdotter & Bäckman, 1989; Verhaeghen et al., 1992; Willis et al., 2006). Benefits from memory training may last from six months to five years (Verhaeghen et al., 1992; Willis et al., 2006). Memory training can transfer to daily life when participants are given homework practice and training in using techniques in daily life and novel situations (McDaniel & Bugg, 2012). Small group interventions, memory education, and relatively short sessions (e.g. 90 minutes or less) are other important components of training programs (Verhaeghen et al., 1992). Memory training also improves subjective memory functioning but effect sizes are smaller (.30) compared to the effect on objective test performance (Floyd & Scogin, 1997). We chose to implement mnemonic methods over computerized memory training programs because the former have a longer history of implementation in aging populations and have more empirical evidence supporting their use in older adults. The MET program in the current proposal includes evidence-based techniques and approaches to facilitate transfer of new knowledge to participants' everyday lives.

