Power analysis: The power analysis is focused on the primary aim of the study to assess whether the KK+KY and MET groups demonstrate comparable improvement in memory performance. We plan to enroll a total of 100 women in the study, anticipating an attrition rate of at most 10% based on our previous studies. Thus, we will most likely have a total of 90 completers. With a sample size of 45 per group, we achieve 80% power to detect equivalence within a margin of equivalence of 0.62, when the true difference between the means is assumed to be zero. In the PI's previous study using similar interventions on older adults with MCI, a between-group effect size of 0.3-0.4 was observed for the memory measures. In the proposed study, the target population is women with high risk for AD, hence we believe that the proposed sample size will have sufficient power to address the primary hypothesis of the study. With this sample size, we can also expect to detect an effect size of 0.60 at a significance level of 0.05 and 80% power for the secondary outcome measure (executive functioning). We intend to test the secondary outcomes adjusting for multiple comparisons using the Benjamini-Hochberg false discovery rate approach (which is more powerful than the simple Bonferroni correction). Further, we will report results of all proposed analyses and conclusions will be based on the pattern of results.

Data management: Data management and analysis support will be provided by the UCLA Semel Institute Statistical Core (SI-Stat) ([name]). The SI-Stat will provide needed software and technical support with a data manager operating under the supervision of [name]. The SI-Stat has a Dell PC computer network with

automated CD R/W backup and is set up for medium to large-scale data processing and analysis using available commercial database and statistical software. **1. Randomization.** Randomization schedules will be prepared in a masked manner by the statistician. **2. Data submission and quality control.** Data forms will be delivered from the originating location to the central data unit within one week of being generated. When errors, omissions, or unclear information is detected on the paper forms, a copy will be returned for corrections. The data manager will generate monthly reports summarizing missing and incorrect data will be sent to the PI.

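### Memory is sized as an equivalence question (margin 0.62), but the planned analysis contains only difference tests, and the hypothesis and design text ask other questions

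*Combined protocol and SAP*

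**What the plan says.** Four places in the protocol describe the main memory question, and they differ.

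- **Power analysis.** The primary aim is "to assess whether the KK+KY and MET groups demonstrate comparable improvement in memory performance". With 45 completers per group and a true difference of zero, "we achieve 80% power to detect equivalence within a margin of equivalence of 0.62". The unit of 0.62, its justification and the significance level of the equivalence test are not given. The same paragraph recalls that in an earlier trial of similar interventions "a between-group effect size of 0.3-0.4 was observed for the memory measures".
- **Hypothesis 1.** "Improved memory performance will be observed in women receiving KK+KY and MET at 12 weeks compared to baseline". This is change over time and makes no comparison between arms.
- **Study Design, rationale for duration and follow-up.** The trial is to test whether KK+KY is superior to MET on cognitive functioning, among other outcomes.
- **Data analysis and its Primary outcome paragraph.** Memory domain z-scores go into a linear mixed model with a random intercept. "The fixed components of the models will include effects of group and time and a group X time interaction". Pairwise comparisons of visits and of arms are described as post hoc. All significance tests are two-sided, with 0.05 for primary analyses and Bonferroni correction for post hoc ones. The groups are compared on their time course at 12 weeks and at 6 and 12 months. Neither section mentions a margin, an equivalence test or a confidence interval rule, and the margin appears nowhere else.

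**The concern.** An equivalence claim needs its own decision rule: the confidence interval for the between-arm difference must lie inside a pre-stated margin. A test of no difference answers another question. A non-significant group-by-time term may only mean that the estimate is imprecise, and gains in both arms are compatible with one arm gaining much more than the other.

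Without a rule, p>0.05 or two within-arm gains could be reported as comparability with no defined error rate. Equally, p<0.05 could be reported as a difference although the interval lies inside the margin. The power paragraph adds to the latitude by saying that conclusions will rest on the overall pattern of results. This concerns the trial's primary conclusion.

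**Working it through.** **Inputs.** From Power analysis: 45 per arm, margin 0.62, true difference 0, power 80%, earlier effect 0.3–0.4. From Data analysis: two-sided 0.05. Assumed: SD 1 for the analysed contrast. The plan scales each test to SD 1 but gives no SD for the averaged composite or its change.

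**Reproducing the 80%.**
- SE = √(2/45) = 0.2108.
- TOST power at zero difference, each one-sided test at 5%: 2Φ(0.62/0.2108 − 1.645) − 1 = 2Φ(1.296) − 1 = 80.5%. The exact t version (88 df) gives 79.7%.
- At 2.5% per one-sided test, which corresponds to a 95% interval: 67.3% (normal) or 65.7% (exact t), needing 56 per arm.
- 45/(1 − 0.10) = 50 per arm, or 100 enrolled, as stated.

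So the stated figure is a TOST figure at one-sided 5%, i.e. a 90% interval, a level that the Data analysis section never states.

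**How often the two questions disagree, SD 1.** The model is a single uncorrected 12-week contrast, d being the observed difference.
- p>0.05 if |d| < 1.987 × 0.2108 = 0.419.
- Equivalence is shown if |d| < 0.62 − 1.662 × 0.2108 = 0.62 − 0.350 = 0.270.
- Results between 0.270 and 0.419 are non-significant without showing equivalence.

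The percentages average these rules over the sampling distribution of the pooled SD:

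| True difference | p>0.05 | Equivalence shown (TOST) | p>0.05, equivalence not shown |
|---|---|---|---|
| 0 | 95.0% | 79.7% | 15.3% |
| 0.3 | 70.9% | 44.1% | 26.8% |
| 0.4 | 53.3% | 27.0% | 26.3% |
| 0.62 | 17.1% | 5.0% | – |

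In the last row the arms truly differ by the whole margin. TOST wrongly declares equivalence 5% of the time; reading p>0.05 as comparability would do so 17% of the time.

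**Change from baseline, with 0.62 in composite-SD units.** The contrast then has SD √(2(1 − r)), where r is the correlation between baseline and week 12. The documents give no r, so a range is shown:

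| r | SD | p>0.05 at true 0.62 | TOST power at 0 | At true 0.3: p>0.05, no equivalence | At true 0.3: p<0.05, equivalence shown |
|---|---|---|---|---|---|
| .4 | 1.095 | 24% | 69% | 36.7% | 0.0% |
| .5 | 1.000 | 17% | 80% | 26.8% | 0.0% |
| .6 | 0.894 | 10% | 89% | 14.0% | 0.5% |
| .7 | 0.775 | 4% | 97% | 1.9% | 8.0% |
| .8 | 0.632 | 0.4% | 99.7% | 0.0% | 37.4% |

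As r rises, the disagreement shrinks and then reverses: at r = .8 the usual conflict is a significant difference inside the margin. The direction thus depends on quantities the plan does not state.

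**The case against.** **The planned model already yields the contrast and its interval.** True. What is missing is the rule for reading it, which makes the repair cheap.

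**The power paragraph may be the outlier.** Aim 1 is not comparative, and the comparisons between times do test Hypothesis 1. This stands, so the fix leaves either route open. But the 80% then refers to a question the trial does not ask.

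**The figures do not model the stated test.** In part true. They use one uncorrected 12-week contrast, whereas the plan also has a group-by-time term over four time points. If the contrast belonged to a Bonferroni set of, say, three, the 15%, 27% and 26% would become 19%, 40% and 43%. The figures illustrate the gap; they do not forecast this trial. Whether the contrast belongs to the post hoc set is itself unclear: the general model description suggests so, while the Primary outcome paragraph names the 12-week group comparison.

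**It is a pilot.** The protocol does use that word, but it still claims 80% power for a formal equivalence question.

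A reader might also infer more than the text supports:
- *That the investigators intend to read non-significance as equivalence.* Nowhere is this said; the text merely fails to exclude it.
- *That a margin above the earlier 0.3–0.4 effect is a fault in itself.* It is not: a margin no larger than that effect would make equivalence nearly unattainable if the effect were real. The tension lies in assuming a true difference of zero. The 0.31 SD net benefit of memory training over control, cited under Memory Enhancement Training, is the more telling comparison, but only if 0.62 is in comparable units.
- *That the sample size is miscalculated.* The 80% reproduces.

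**Conclusion.** The point holds and should be fixed before analysis. The trial is sized for equivalence on memory, its stated tests are difference tests, Hypothesis 1 is change from baseline and the design section speaks of superiority. As written, the analysis cannot deliver the conclusion to which the 80% power refers. That mismatch can be read from the text and rests on no assumption.

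The size does rest on assumptions. With SD 1, p>0.05 without equivalence occurs in 15% to 27% of trials at true differences of 0 to 0.4, and p>0.05 occurs in 17% at a true difference equal to the margin. For a change-from-baseline contrast the latter figure runs from 24% at r = .4 to 0.4% at r = .8. It would therefore be wrong to say that a difference test is always the more lenient route to a claim of comparability.

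**What to change.** Declare one primary memory objective and align Hypothesis 1, the Study Design text, the Data analysis section and the Power analysis paragraph with it.

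If the objective is equivalence:
1. Make the primary contrast the 12-week KK+KY minus MET difference in change in the memory composite, from the planned mixed model. Baseline adjustment could add precision but would change that model.
2. Report a 90% confidence interval and conclude equivalence only if it lies wholly within the margin (TOST at one-sided 5%, which the stated 80% requires). A 95% interval would give about 66% power.
3. State that this contrast is primary and outside the Bonferroni-corrected post hoc set.
4. State that p>0.05 is not evidence of comparability, and how p<0.05 with the interval inside the margin will be read.
5. Give the unit of 0.62 and justify it, in particular against the 0.31 SD training effect if the units are comparable.
6. Keep the within-arm change of Hypothesis 1 as a separately labelled analysis that is not evidence of comparability.

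If equivalence is not intended, rewrite the power paragraph for the intended hypothesis.

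**Cost.** Mainly wording. The number of participants can stay only if the margin of 0.62, the one-sided 5% level and an SD of about 1 or less all hold; for change scores at r = .4, power is 69%. A smaller margin could require more participants. With SD 1, power is 80% only at a true difference of zero, and 44% and 27% at 0.3 and 0.4; the protocol should say so. Whether the neuropsychological battery is scheduled at week 12 is a separate question, but the contrast depends on it.
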